	
two consecutive increases measured in the same laboratory; and/or
 
 An increase in the number of metastatic sites on follow-up imaging assessments. 	
SECONDARY OBJECTIVES AND ENDPOINTS		
Secondary objectives	Endpoints	Evaluation time
a) Biochemical relapse-free survival	
A PSA > 0.2 ng/mL after the post-treatment nadir (or PSA > nadir + 0.2 ng/mL if nadir > 0.2 ng/mL).
 
For patients without a history of prostatectomy, biochemical recurrence is defined by:
 
 A PSA > pre-treatment nadir AND A PSA > 0.2 ng/mL after the post-treatment nadir 	2 years
b) Time to resumption of hormone therapy	Resumption of hormone therapy	5 years
c) Time to initiation of any subsequent treatment	Resumption of any treatment	5 years
d) Assessment of toxicity (acute toxicity assessed 1 month after the end of radiotherapy, and late toxicity assessed at 2 years), with particular attention to gastrointestinal events	NCI-CTC-AE v4.0 scale	5 years
e) Site of relapse: within the irradiated field or at distant (non-irradiated) sites	
At least one morphological imaging (depending on recurrence location and center practice):
 
 Abdominopelvic CT scan and/or Pelvic MRI and/or Bone scintigraphy and/or FCH-PET (post-treatment PET will be optional). 	5 years
f) Overall survival	Overall survival	5 years
g) Quality of life	QLQ-C30 + QLQ-PR25	5 years
h) Optional ancillary biological study: validation of a novel mutational signature in patients with oligometastatic prostate cancer treated with radiotherapy		
INCLUSION CRITERIA	
 Histologically proven adenocarcinoma of the prostate Patients aged 18 years or more PS 0-1 	

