	
 4) Previous radical treatment to the prostate (radiotherapy or surgery) 5) PSA increase of at least 3 assays in the same laboratory over the last 12 months. 6) 1-5 pelvic lymph node metastases detected with 18FCH-PET. A relapse in the dressing prostatectomy is associated possible. 7) Upper limit of lymph node metastases: aortic bifurcation 8) Respect of dosimetry constraints to organs at risk 9) Treatment with hormone therapy may be started before inclusion, to a maximum of three months prior to Day 1 of radiotherapy. This hormone will necessarily be preceded by a free interval treatment of at least 6 months since the last injection, by adding the duration of action of this predictable injection (1, 3 or 6 months) 10) Patient affiliated to a social security scheme 11) Patient Information and written informed consent form signed
NON-INCLUSION CRITERIA	
 1) Bone or visceral metastatic relapse associated 2) Para-aortic nodal relapse (the upper limit is tolerated aortic bifurcation) 3) More than 5 lymph node metastases 4) Proof of metastases at initial diagnosis 5) Evidence of distant metastases in the pelvic lymph nodes or outside the prostate bed prior pelvic lymph nodes irradiation. Irradiation of the bed of the prostate is not an exclusion criterion, but the junction between prior irradiation bed prostatectomy and radiation field pelvic lymph nodes should be examined carefully 6) Castration resistance defined by clinical or biochemical progression despite a combined androgen blockade 7) Known contraindications to pelvic irradiation (eg, chronic inflammatory bowel disease, ...) 8) Known contraindications to hormone therapy, according to standard recommendations in force 9) Serious hypertension not controlled by appropriate treatment 10) Other concomitant cancer or history of cancer (within 5 years prior to study entry), except basal cell or squamous cell carcinomas of the skin. 11) Patient with a psychological, familial, sociological or geographical potentially hampering compliance with the study protocol and follow-up schedule 12) Patient already included in another interventional study involving the approval of a cpp during his screening for the study Oligopelvis 13) Private person of liberty or major trust

E) INVESTIGATIONAL TREATMENT DESCRIPTION

Experimental procedure

- **Radiation therapy**

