
(p = 0.059). In this case the DSMB will meet to analyze the toxicity and decide whether to continue the study.

G) STUDY CALENDAR

DURATION OF INCLUSION PERIOD	24 months
TREATMENT DURATION	ADT + IG-IMRT: 6 months of ADT / 6 to 7 weeks (30 fractions) of IG-IMRT
POST TREATMENT FOLLOW UP	10 years
PRIMARY ENDPOINT ANALYSIS EXPECTED DURATION	2 years
STUDY COMPLETION DURATION (INCLUDING FU PERIOD)	12,5 years

SCHEDULE OF STUDY ASSESSMENTS

Visits	Inclusion Max 2 months prior to RT day 1	Treatment period	follow-up		
			M1 1 month after end of RT	Before progression Every 6 months during 2 years	After progression Every 6 months until death
Inclusion/exclusion criteria	X				
Signed consent form	X				
Inclusion (max 2 months prior to RT)	X				
FCH PET	X (a)				X (b)
Physical examination with PS	X	X (d)	X	X	X
Prior history, tumor characteristics	X				
Blood Pressure	X	X (d)	X	X	
Acute toxicity during ADT and RT (f)		X (d)	X		
Late toxicity (f)				X	
QLQ-C30 et QLQ-PR25	X		X	X	
PSA	X		X (f)	X (f)	X (f)
Testosterone	X (g)		X	X	X
ADT (c) + RT		X			

(a) maximum 3 months prior to initiation of ADT

(b) at progression

(c) 6 months treatment starting on RT day 1 or maximum 3 months prior to RT

(d) once per week during RT

(e) biochemical progression = PSA higher than inclusion PSA with 2 successive rises in the same laboratory

(f) NCI-CTCAE v4.0

(g) 28 days prior to ADT

STUDY DIAGRAM

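### For patients without prostatectomy, the secondary biochemical relapse rule omits the nadir-plus-0.2 clause, so once the post-treatment nadir is above 0.2 ng/mL a smaller rise, even a trivial one, can count as relapse

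*Combined protocol and SAP*

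**What the plan says.** Section C, secondary endpoint a) (biochemical relapse-free survival, evaluated at 2 years), first gives a general rule: "A PSA > 0.2 ng/mL after the post-treatment nadir (or PSA > nadir + 0.2 ng/mL if nadir > 0.2 ng/mL". The threshold is thus 0.2 ng/mL for a patient whose post-treatment nadir is at or below 0.2, and the nadir plus 0.2 for a patient whose nadir is higher.

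A second rule follows: "For patients without a history of prostatectomy, biochemical recurrence is defined by" two joint conditions. The first is "A PSA > pre-treatment nadir AND" and the second is "A PSA > 0.2 ng/mL after the post-treatment nadir". The second condition repeats the opening of the general rule and stops before the parenthesis. Nothing states whether the parenthesis carries over, and the term pre-treatment nadir is not defined.

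Patients without prostatectomy can enter the trial: inclusion criterion 4 accepts "Previous radical treatment to the prostate (radiotherapy or surgery").

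**The concern.** The clause in the general rule has a clear purpose. A patient whose PSA never falls to 0.2 ng/mL should not be counted as relapsed merely for staying above 0.2; a rise of more than 0.2 from his own nadir is needed. The definition for patients without prostatectomy drops that protection.

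At stake is how relapse is dated in this group. Events could be called on small rises that the general rule would ignore, which pulls down the pooled 2-year estimate for this endpoint. Two analysts could also code the same data differently, one carrying the clause over and one not.

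**Working it through.** The plan states no figure that depends on this rule, so the check compares the two definitions.

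**Inputs.** Both rules are those of secondary endpoint a). The documents give no nadir values, so the pairs in the table are assumed for illustration, over 0.1 to 1.0 ng/mL. Pre is the pre-treatment nadir, read here as the lowest PSA before study treatment; post is the post-treatment nadir.

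**Thresholds (ng/mL).**
- General rule: G = 0.2 if post ≤ 0.2; G = post + 0.2 if post > 0.2.
- Without prostatectomy, as written: PSA must exceed max(pre, 0.2).
- Without prostatectomy, clause restored: PSA must exceed max(pre, G).

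**Rise needed above the nadir when post > 0.2.**
- As written: every later value is at least post, hence above 0.2, so the second condition has no effect. Rise = max(0, pre − post).
- Clause restored: rise = max(0.2, pre − post).
- The two differ exactly when pre < post + 0.2.

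When post ≤ 0.2 the two versions are identical.

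| Pre | Post | As written: relapse if PSA | Rise | Clause restored: relapse if PSA | Rise | General rule: relapse if PSA |
|---|---|---|---|---|---|---|
| 0.3 | 0.5 | any value above 0.5* | > 0* | > 0.7 | > 0.2 | > 0.7 |
| 0.1 | 0.25 | any value above 0.25* | > 0* | > 0.45 | > 0.2 | > 0.45 |
| 0.3 | 1.0 | any value above 1.0* | > 0* | > 1.2 | > 0.2 | > 1.2 |
| 0.5 | 0.5 | > 0.5 | > 0 | > 0.7 | > 0.2 | > 0.7 |
| 0.6 | 0.5 | > 0.6 | > 0.1 | > 0.7 | > 0.2 | > 0.7 |
| 1.0 | 0.5 | > 1.0 | > 0.5 | > 1.0 | > 0.5 | > 0.7 |
| 0.5 | 0.1 | > 0.5 | > 0.4 | > 0.5 | > 0.4 | > 0.2 |
| 0.1 | 0.1 | > 0.2 | > 0.1 | > 0.2 | > 0.1 | > 0.2 |

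*A flat repeat of the nadir also qualifies if the nadir is dated at its first occurrence.

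**Direction of the error.** Any PSA that meets the clause-restored rule also meets the rule as written: if PSA > post + 0.2 and post > 0.2, then PSA > 0.2. So the relapse date as written is never later and may be earlier. The 2-year status changes only for a patient who passes the lower threshold by 24 months and does not pass the higher one by then. For other affected patients only the date moves.

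**Whether another section repairs it.** The requirement for two rises belongs to the primary endpoint and to footnote (e) of the assessment schedule: "biochemical progression = PSA higher than inclusion PSA with 2 successive rises in the same laboratory". Neither is tied to endpoint a). Section F defines progression-free and overall survival only. It refers to a section 8.5.1 for biochemical-clinical failure; that section is not in the supplied text, and the reference concerns the composite event.

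**The case against.** The best defence is that the second condition is shorthand. The general sentence is not limited to prostatectomy patients. The later condition repeats its opening words and adds a further requirement, which looks like an extra safeguard for men with a prostate in place. The table supports this as the likely intention: with the clause restored, this group's threshold is never below the general one, whereas as written it falls below it in the first five rows. The sponsor may equally have meant a rise of 0.2 from the nadir. Neither reading is stated, however, and the group is given what reads as a complete definition. The defence is therefore a reason to clarify the text.

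Two narrower points stand. First, relapse with no rise at all depends on dating the nadir at its first occurrence, which the plan does not specify. The firmer statement is that any rise, however small, would do. Second, if pre-treatment nadir was meant as the pre-treatment PSA value used in the primary endpoint, a post-treatment nadir above it would mean that PSA never fell below baseline, and calling that relapse would not be clearly wrong. The missing definition is therefore part of the problem.

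A reader might infer that patients with a prostate in place are generally counted as relapsed at the first assay after nadir. The rule does that only, at most, where the post-treatment nadir exceeds both 0.2 and the pre-treatment nadir. A reader might also infer that the two surgical groups can no longer be compared. The trial is single-arm, no analysis by prostatectomy status is planned, and the plan gives the groups different definitions by design.

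**Conclusion.** The rule is wrong as written, within narrow limits. For a patient without prostatectomy whose post-treatment nadir is above 0.2 ng/mL, the rise needed for relapse is below 0.2 ng/mL whenever the pre-treatment nadir is less than the post-treatment nadir plus 0.2. It shrinks to any rise when the post-treatment nadir equals or exceeds the pre-treatment nadir. The error runs one way: relapse too early, and 2-year biochemical relapse-free survival the same or lower.

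The size cannot be derived. The documents give neither the share of patients without prostatectomy nor how often these nadir patterns occur. A reader might multiply assumed shares to get a number of misclassified patients. Such a figure would rest on nothing in the plan, and it would count patients with the nadir pattern, not patients whose 2-year status changes.

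The point affects one secondary endpoint. The primary endpoint has its own PSA criterion, with two consecutive increases above the pre-treatment value. The sample size section speaks loosely of biochemical relapse; I take its 39-of-63 rule to refer to the primary endpoint. On that basis the rule and the sample size are unaffected. The conclusion rests on a literal reading of the definition and on taking the pre-treatment nadir as a value from before study treatment.

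**What to change.** Carry the clause into the second condition for patients without prostatectomy: PSA above the pre-treatment nadir, AND PSA above 0.2 ng/mL if the post-treatment nadir is at or below 0.2, or above the post-treatment nadir plus 0.2 ng/mL if that nadir is above 0.2. Writing the two nadir cases as mutually exclusive prevents the 0.2 threshold from being applied to a patient with a higher nadir.

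The sponsor should also define the pre-treatment nadir: from which period it is taken, whether values under earlier hormone courses count (inclusion criterion 9 allows for such courses), and how it differs from the pre-treatment PSA value in the primary endpoint. The same note should say how the post-treatment nadir is dated when the lowest value recurs.

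The cost is one line in the endpoint table and a short definition. The amended second condition needs no new assessments, since PSA is already scheduled one month after radiotherapy and every 6 months for 2 years.

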PROTOCOL OLIGOPELVIS 1_GETUG P07

A) CLINICAL TRIAL IDENTIFICATION

STUDY TITLE	Multicentric phase II study of high-dose radiotherapy and hormone therapy in oligometastatic relapses of the pelvic lymph nodes of prostate cancer
SHORT TITLE	OLIGOPELVIS 1_GETUGP 07
INVESTIGATOR COORDINATOR	Pr [name]
ID-RCB	2014-A00138-39
REF ANSM	140494B-12 AUTORISATION 13/06/14
ETHICS COMMITTEE NAME	CPP OUEST-IV
REF ETHICS COMMITTEE	19/14 SESSION OF 13/05/14
N° CLINICAL TRIAL.GOV	NCT02274779

B) STUDY BACKGROUND

There is a growing body of evidence reporting the existence of a subset of prostate cancer patients who, at relapse, present with a limited number of metastases (fewer than five lesions). This oligometastatic state has also been identified in other tumor types, such as melanoma, soft tissue sarcoma, liver, lung, and breast cancers, and has led to a shift in management toward more aggressive local treatments, including surgical resection.

Positron Emission Tomography–Computed Tomography (PET-CT), using tracers such as choline or acetate, has proven to be a reliable tool for detecting oligometastatic disease following biochemical recurrence in prostate cancer. For patients in this setting, an intensified therapeutic approach—combining androgen deprivation therapy (ADT) with high-dose radiation therapy directed at PET-CT-detected lesions—may be proposed.

This strategy has the potential to prolong the interval between successive courses of ADT or, in selected patients with a limited metastatic burden, may even offer the possibility of cure.

In this study, the investigators aim to evaluate the 2-year biochemical or clinical relapse-free survival of prostate cancer patients with 1 to 5 oligometastases treated concomitantly with high-dose conformal radiation therapy and LH-RH agonists.

C) STUDY INFORMATION

INDICATION	Oligometastatic lymph nodes pelvic prostate cancer patients	
METHODOLOGY	Non randomized, prospective, national multicentre, phase II	
Primary Objective and Endpoint		
Primary objective	Endpoint	Evaluation time
The primary objective is to evaluate the biochemical or clinical relapse-free survival at 2 years.	The primary endpoint is the 2-year relapse-free survival probability. Biochemical or clinical relapse is defined as: 
 • A PSA level higher than the pre-treatment PSA value, confirmed by 	2 years

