A simultaneous integrated boost will be applied to PTVs. It will be administered 5 days per week during 5 to 7 weeks.

The radiation therapy will start three months (+/- 15 days) after the first injection of IADT.

General recommendations

The use of intensity-modulated radiation therapy (IMRT) is mandatory.

Irradiation will be delivered to patients with an empty rectum. It is recommended that the patient empties his bladder and rectum one hour before the planning CT scan and before each radiotherapy treatment, and then drink at least 1/3 L of water after voiding. The one-hour delay will be adapted to the patient's continence.

If the prostate bed has been previously irradiated, it is recommended that the irradiation be delivered with the bladder empty in order to avoid re-irradiation of the bladder due to overlapping fields.

Daily verification of patient's organ positioning using IGRT is mandatory.

The use of a record and verify processing software is mandatory.

Preparation of treatment

A planning CT of the pelvic cavity that includes all of the pelvic lymph nodes will be performed in the supine position, with intravenous contrast agent to aid visualization of the pelvic vessels. Oral contrast agent will also be administered to assist in the determination of the small bowel volume. The minimum CT resolution will be at least 3 mm thick slices every 3 mm, but thinner slices may be necessary for very small volume lymphadenopathy. Merging the CT with pelvic MRI may help to visualize the vascular axes and pelvic lymph nodes.

Fusion with FCH-PET (or PSMA-PET): The FCH-PET (or PSMA-PET) images will be segmented using a threshold adapted to the size of the lymphadenopathy. These images will be used to locate the pathological lymph nodes, but the tumor volume (GTV) will be contoured on the planning CT.

Target Volumes

a) Metastatic lymph nodes

GTV1 to GTV5 will be delineated on the planning CT-scan with the aid of FCH or PSMA PET.

A margin of 3-5 mm around the GTVs will define the clinical target volumes (CTVs).

An additional margin of 3-5 mm around the CTVs will define the planned target volumes (PTVs). The intersection between PTVs and small intestine will be removed from the PTVs.

b) Whole pelvic lymph node irradiation

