- DVH for intestine, bladder and rectal wall, PTV and CTV that meet dose constraints;
- a statement that patients will be treated with an approved daily image guidance technique.

All treatment plans will be sent via a web-based platform for central review and approval prior to beginning radiotherapy.

Quality control of IMRT: all IMRT plans will undergo quality assurance evaluation with ion chamber measurements or an equivalent method of dose verification to verify the absolute dose for each IMRT field, and film dosimetry to measure the relative dose for each IMRT field, as is standard clinical practice. An independent monitor unit calculation may be substituted for ion chamber dosimetry when available.

Management of previously irradiated patients

When the prostate/prostate bed has been irradiated previously, a cumulative dosimetric study will be performed to assess for radiotherapy volumes overlap, and the 20 Gy isodose will be drawn.

If any PTV1-5 has received more than 20 Gy during a previous course of irradiation, the patient should be excluded from the study.

If less than 20 Gy was delivered to PTV1-5, the lower limit of PLN PTV will be restricted to PTV1-5. No modification of the dose constraints will be applied.

Dose adjustment

No dose adjustments will be made.

- **Hormonotherapy**

Hormone therapy is recommended Eligard 45 mg acting for 6 months.

It will be ideally administered the day of start of radiation therapy or within 3 months before the first day of radiotherapy.

Nevertheless, free prescription is left to investigators.

When using other hormonal strategies (anti-androgen agonists, LHRH antagonists or LHRH), an administration for six months will be critical.

F) STATISTICAL CONSIDERATIONS

SAMPLE SIZE DETERMINATION

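### The radiotherapy section fixes a three-month ADT lead-in that the hormone section and schedule do not require, and the PSA reference for relapse is not tied to a pre-ADT value

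*Combined protocol and SAP*

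**What the plan says.** Four places in the combined protocol and SAP govern when ADT starts relative to RT.

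- Section E, Radiation therapy: "The radiation therapy will start three months (+/- 15 days) after the first injection of IADT". The sentence is mandatory, carries a numeric tolerance and has no exception.
- Section E, Hormonotherapy: "It will be ideally administered the day of start of radiation therapy or within 3 months before the first day of radiotherapy". It goes on: "Nevertheless, free prescription is left to investigators".
- Section G, schedule of study assessments, footnote (c): "6 months treatment starting on RT day 1 or maximum 3 months prior to RT".
- Section C, inclusion criterion 9: "Treatment with hormone therapy may be started before inclusion, to a maximum of three months prior to Day 1 of radiotherapy".

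The schedule also limits the time from inclusion to radiotherapy: "Inclusion Max 2 months prior to RT".

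The PSA reference for relapse is worded in two ways. The primary endpoint in section C uses "A PSA level higher than the pre-treatment PSA value, confirmed by" two consecutive rises. Footnote (e) of the schedule reads "biochemical progression = PSA higher than inclusion PSA with 2 successive rises in the same laboratory".

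**The concern.** A centre that gives the first injection on RT day 1 follows the hormone section and footnote (c), yet breaches the radiotherapy section. A centre that uses the full tolerance of the radiotherapy section goes past the 3-month cap. Nothing in the text says which rule prevails, so compliance with the regimen cannot be judged in the same way at every centre.

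A second, separate point bears on the primary endpoint. Relapse is judged against a baseline PSA, and ADT may begin before inclusion. If the inclusion PSA is drawn after ADT has begun, it is not a pre-treatment value, and the two wordings of the reference can give one patient two different thresholds. At stake is whether the 2-year relapse-free proportion is measured against the same kind of baseline in every patient.

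**Working it through.** The documents state no figure for the overlap of these rules, so there is none to reproduce. The check sets the intervals side by side.

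**Inputs.** RT rule: 3 months ± 15 days after first ADT (section E, Radiation therapy). Hormone rule: 0 to 3 months before RT (section E, Hormonotherapy; footnote (c)). Cap: 3 months before RT (criterion 9). Inclusion to RT: 0 to 2 months (schedule). Assumptions: one month is 30.44 days, and IADT in the radiotherapy section means the same study hormone therapy.

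**Step 1, the windows in days.** 3 × 30.44 = 91.3.

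| Rule | Lead-in from first ADT to RT |
|---|---|
| Radiotherapy section | 91.3 − 15 = 76.3 to 91.3 + 15 = 106.3 |
| Hormone section, footnote (c) | 0 to 91.3 |
| Criterion 9 | at most 91.3 |

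**Step 2, where they agree.** The common range is 76.3 to 91.3 days, about 2.5 to 3.0 months. It is 15 days wide, or 15 / 91.3 = 16% of the 0-to-91-day window.

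**Step 3, where they conflict.** From 0 to 76 days, a start that the hormone section and footnote (c) allow breaches the radiotherapy section; a same-day start misses by the full 76 days. From 91 to 106 days, a start that the radiotherapy section allows exceeds the cap. This second conflict is a minor one of tolerance.

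**Step 4, ADT exposure on the inclusion date.** Exposure = lead-in − time from inclusion to RT, where positive.

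- Lead-in 0: none.
- Lead-in 3 months: 3 − 2 = 1 to 3 − 0 = 3 months.
- Whole radiotherapy-section window: 2.5 − 2 = 0.5 to 3.5 − 0 = 3.5 months.

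Any lead-in over 2 months therefore puts the inclusion date after the ADT start. Shorter lead-ins can do so too if inclusion is close to RT. The possibility exists under either timing rule and does not depend on the radiotherapy sentence.

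**Step 5, from inclusion date to PSA sample.** The inclusion date does not date the sample. Other items in the Inclusion column are timed to ADT: footnote (a) places the PET scan within 3 months before ADT, and footnote (g) places testosterone 28 days before ADT. The inclusion PSA has no such anchor. It may be drawn before or after the first injection, so the two reference values may agree or may differ.

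**Step 6, design figures.** Neither point enters the sample-size calculation. The rule of 39 or more relapse-free among 63 gives an exact one-sided alpha of 3.85% and power of 93.56%, against the stated 3.85% and 93.5%. Allowing for 10% loss, 63 / 0.90 = 70, as stated.

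**The case against.** The best defence is that the flexibility is deliberate. The hormone section, footnote (c) and criterion 9 share the 3-month maximum, and investigators are left free in prescribing. A lead-in of 2.5 to 3.0 months satisfies everything, so the protocol can be carried out as written. This stands in part: the rules are not impossible to follow together. But the free-prescription sentence sits between the recommended product and the paragraph on other hormonal strategies, so it most naturally concerns the choice of agent. Even if it covers ADT timing, it does not amend the RT start rule.

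A reader might infer that the contradiction is what makes the amount of ADT after RT variable. Six months of ADT would end 6 − 3 = 3 to 6 − 0 = 6 months after RT starts. The hormone section and footnote (c) allow that whole spread by themselves, and it would remain under a single 0-to-3-month window. It is not a consequence of the conflict.

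A reader might also infer that, with a long lead-in, the inclusion PSA is always an on-ADT value and always differs from the pre-treatment PSA. Footnotes (a) and (g) show that Inclusion-column items can predate ADT, so the documents support only that the values may differ.

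It is also fair to say that footnote (e) is loosely attached. No cell in the schedule refers to it; the follow-up PSA cells carry (f), which is the toxicity scale. The primary endpoint itself is defined in section C. Yet that definition does not say which treatment its baseline precedes or which sample supplies it, so footnote (e) remains a competing definition. Finally, a lower reference calls relapse sooner and so makes rejecting the null hypothesis harder. That limits the worry about a falsely positive trial but does not make thresholds comparable between patients.

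**Conclusion.** The plan is internally inconsistent as written; no figure in it is miscalculated. An ADT start on RT day 1 is both named as acceptable and ruled out, by about 76 days, and lead-ins of 3.0 to 3.5 months pass one rule and exceed another. Only about 2.5 to 3.0 months satisfies all of them.

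The PSA point is separate and would outlast a correction of the timing sentence. Because ADT may precede inclusion, the baseline in footnote (e) may be an on-ADT value and may not match the one in the primary endpoint. The direction (relapse called sooner in those patients) rests on the assumption that ADT lowers PSA.

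The documents give neither the number of patients affected nor any PSA values, so the effect on the 2-year rate cannot be sized, and no claim that the result is materially biased is supported. The sample size and decision rule stand. The point is worth correcting because it touches the primary-endpoint definition and costs only wording.

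**What to change.** 1. State one ADT-to-RT window in criterion 9, both parts of section E and footnote (c). The simplest course is to replace the radiotherapy sentence with: ADT starts on RT day 1 or at most 3 months before. The other places already support this. If a three-month lead-in is what is intended, amend criterion 9, the hormone section and footnote (c) instead, and make the cap agree with the tolerance.
2. Under either window, define the reference PSA in the primary endpoint and in footnote (e) as the last value before the first ADT injection. Criterion 5 already requires rising PSA assays in the preceding 12 months, so such a value should usually be on file.
3. Report the actual ADT-to-RT interval alongside the 2-year result.

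The cost is one wording amendment and a notice to centres, with no new visit, probably no new sample, and no change to the sample size or decision rule. If treatment is already complete, items 2 and 3 can still be settled in the analysis plan.
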